4.3. Subject Recruitment, Enrollment and Screening

The recruitment for this study will include participants from Mayo Clinic Florida patients and staff, and collaboration with the University of North Florida.

In 2019, approximately 284 patients had skin patch tests performed at Mayo Clinic Department of Dermatology in Jacksonville Florida. Among these patients, 17 were identified Black or African American with a Fitzpatrick score of 5-6, and 32 were identified as Hispanic or Latino with a Fitzpatrick score of 3-6.

Additionally, we will advertise for a healthy control group throughout Mayo Clinic Florida campus as well as the University of North Florida. In 2019, the University of North Florida student population enrollment was reported at approximately 17,117 students. The distribution of population for minority population of interest is 10% (1,684) Black or African American, 13.3% (2,280) Hispanic or Latino, and 5% (853) two or more races. Potential participants can contact the study coordinator listed in the flyer and/or electronic display to further inquire on eligibility criteria and study questions.

Thus, we estimate that from a pool of 49 eligible patients in Mayo Clinic Florida per year, the robust minority population of employees at Mayo Clinic and student population at University of North Florida, we can achieve full enrollment.

We will monitor enrollment bi-weekly and will hold calls with the study team to clarify questions about eligibility and ensure robust recruitment. If recruitment falls short of numerically defined targets, we will assess reasons for slow accrual and adjust the protocol accordingly.

Patients who have undergone previous patch testing will be screened by an experienced study coordinator for participants with a Fitzpatrick skin types 4 through 6 and eligibility criteria. This study coordinator will call the patient to discuss the study, eligibility, and study logistics, and then will plan to meet the patient at their next visit to the clinic to review and sign the consent (if the patient wishes to participate and is eligible).

Potential participants who answer the advertisement will have a call scheduled with the study coordinator to discuss the study, eligibility, and study logistics. Based on the potential participant's agreement, the study coordinator will schedule a research visit, as well coordinate with the Dermatology medical assistants to schedule the patch testing procedures.

The study coordinators are skilled in presenting the trial information without bias or pressure and in a culturally appropriate manner. Translators will be used as needed. Study coordinators will ask those patients who remain initially undecided if they may contact them again at a determined timeframe to review again and ask further questions. Screening and enrollment failures and related reasons for same will be discussed at the monthly review meetings and potential actions will be taken as need. Attention will be paid to adhering to regulatory issues.

4.4. Early Withdrawal of Subjects

4.4.1. When and How to Withdraw Subjects

Participants may withdraw at any point in the study. In the event the test patch is removed early due to possible reaction to an allergen or for another other reason (e.g., removed while bathing), the study team will be notified of the event.

4.4.2. Data Collection and Follow-up for Withdrawn Subjects

Participation is strictly voluntary. The participant will be followed according to protocol to document the reactions if the participant is willing. If the participant is unable or unwilling to continue with protocol procedures, the study records will be noted as such.

5. Test Patch and Allergen Details

5.1. Description of test patch vehicle

The test patch (Finn Chamber) is a non-sterile aluminum chamber mounted on Scanpor tape, which is a hypoallergenic surgical tape with a non-latex adhesive. The tape is made of rayon and polyester fibers.

5.2. Investigational allergens

5.2.1. Primary Test Site (arm 1)

The following ten allergens manufactured by AllergEAZE will be used for patch testing during the study. Potential adverse reactions include pruritus, irritation, skin discoloration, erythema, induration, blistering and ulceration. Pruritus can be managed over-the-counter antihistamines.

While most reactions self-resolve, more severe skin reactions would be managed with topical steroids.

1. Nickel sulfate hexahydrate, 2.5% (18.3%)
2. M. Pereirae resin, 25% / Balsam of Peru (9.2%)
3. Neomycin sulfate, 20% (7.8%)
4. Fragrance mix, 8% (6.7%)
5. Bacitracin, 20% (6.4%)
6. Carba mix, 3% (5.8%)
7. Quaternium-15, 1% (4.4%)
8. Benzoic acid, 5% (3.7%)
9. Propolis, 10% (3.5%)
10. Thiuram mix, 1% (2.8%)

5.2.2. Secondary Test Site (arm 2)

As part of the technology development program, two secondary tests will be used. Each participant will be randomized to one of these two patches.

Combination Patch #1: Standard Panel Array of 10 Allergens Combined into 4 Wells

- 1: Metals: Nickel sulfate hexahydrate
- 2: Fragrance & Taste Enhancers: M. Pereirae resin, 25% / Balsam of Peru + Fragrance mix + Quaternium-15
- 3: Topical/Homeopathic: Neomycin sulfate + Bacitracin + Propolis
- 4: Fungicides: carba mix + Thiuram mix + Benzoic acid

Combination Patch #2: Common Jewelry & Cosmetic Patch

- 1: Common metal allergy: Nickel sulfate hexahydrate
- 2: Cosmetics: M. Pereirae resin, 25% / Balsam of Peru
- 3: Cleaners: Methylchloroisothiazolinone / methylisothiazolinolone
- 4: Fragrance: Fragrance mix

Combination Patch #3: Patient Identified Allergen Profiles

For Phase II and III of the study, the following ten allergens will be added to the pool of 10 unique allergens tested in the primary patch and the combination of allergens offered as a part of the two combination patches.

- Linalool
- P-phenylenediamine
- Benzisothiazolinone, 0.1p
- Methylchloroisothiazolinone / methylisothiazolinone
- Paraben mix
- Formaldehyde
- Tea Tree Oil
- Cobalt Chloride
- Disperse Dye (Blue Mix)
- Gold Sodium Thiosulfate

This patient-driven combination of allergens can have between 1 and 10 individual test sites allowing for measurement of preference for “body burden” and patch test configurations.

5.3. Method for Assigning Allergens to Test Site Regions

To minimize complexity of the randomization process and preparation of the patch test for the primary test site, a total of four randomized placement sequences will be generated. Participants will be assigned to these sequences in consecutive order. This same randomization sequence will be used to randomize the secondary patch option to the participants with participants holding an odd study number receiving Combination #1 and even study numbers receiving #2. Note these two patches are largely identical except for how the allergens are combined with the exception that Combination #2 has methylchloroisothiazolinone / methylisothiazolinone added to it.

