5.6. Masking/Blinding of Study

The medical professional that reads the photographs of the test sites will be blinded to all clinical information including, but not limited to, the allergen's randomized locations, the in-person assessment of the reactions, and any AI predictions on the images. Effectively, the human read of the photograph will only have the photograph available to form all impressions about the reactions.

The reading of the human interpretation of the photographs will occur at least 1 month after the clinical visit to maintain blinding and washout in the event study staff provide a visual impression of the reaction sites via photographic review.

6. Study Procedures

6.1. Prior to Visit 1 and after study consent, the participant will have an opportunity to complete the Patient Journey. For Phases II and III of the study, this patient journey will be distributed to the patient prior to Visit 1 to allow for the data to be summarized. The summarization will include qualitative and quantitative approaches to quantify the self-reported employment profiles, ancestry, and known allergens to identify which allergens that may be more allergenic to the participant.

Visit 1 (Day 1)

Informed consent will be obtained as well as demographic information, medical history, and current medications questionnaire (see Schedule of Events).

A limited physical exam focused on the forearm will be conducted as well as assessment of participant's Fitzpatrick skin type.

A baseline photo will be taken using the smart phone application and the additional camera systems including the full spectrum documentation and photogrammetry acquisition.

A member of the study team will place the primary test patch on the volar aspect of participants' forearm. The patch contains allergens placed in dime-sized wells. The location of the allergens within the patch will be randomized between participants. The study team member will document the location of each allergen.

The smaller, 4 well patch, on the secondary arm will be placed similar manner to the primary test patch.

Tape or waterproof dressing may be used to secure the patch strips. Participant will be given instructions to avoid water contact with patch, and avoidance of sun exposure.

Participants will be allowed to take over the counter histamine blockers to alleviate pruritus.

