6.3. Visit 3 (Day 5)

After about 96 hours (Day 5), the participant will return for a final assessment.

This assessment time is the final (reference criterion) assessment as it is necessary to allow for up to five days for a skin reaction to appear.

At the visit, the medical professional with training in patch testing will review the skin for any reaction and document in the CRF.

A complete set of photos will be taken to document the reactions using the smart phone application and other camera systems.

Participant feedback on the patch testing experience will be documented.

Severe contact dermatitis will be treated with topical steroids if needed.

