There is a block of standard measures of diagnostic performance (e.g., sensitivity, specificity). These statistics will be computed as is customary for similar studies. The calculations will be performed two ways when possible. First, each test site will be assumed to be statistically independent in the rating. For the neural network, this is how the algorithm functions. For the human reading, there may be some correlation among the ratings based on the reactions, if any, that are observed. To address this, an exploratory analysis will be conducted using generalized estimating equations to examine the impact empirically the intercorrelations may have on the estimated precision of the estimates (i.e., confidence interval width).

Safety data will be summarized by tabulating adverse events for the study. These will be categorized according to allergen related or study protocol related.

The secondary test sites include allergens, in novel combinations, that were tested in the primary test site. A secondary analysis will be conducted to quantify the agreement of reactions to the same allergens alone (primary test patch) and in combination (secondary test patch). Kappa will be used to quantify this agreement.

Finally, participant feedback on the study including the wearability of the patch on the forearm will be summarized using standard qualitative methods. This will include the extraction of key themes as well as listing open ended feedback provided to the study team by the participants.

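### No well order is specified for the 4-well patch and no masking for the in-person assessor, so the alone-versus-combination kappa may rest on unmasked grades

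*Combined protocol and SAP*

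**What the plan says.** Section 5.3 sets the rule for allergen positions: "for the primary test site, a total of four randomized placement sequences will be generated", and "Participants will be assigned to these sequences in consecutive order". For the secondary patch it settles which version is worn, with "participants holding an odd study number receiving Combination #1 and even study numbers receiving #2". It gives no order for the wells within either version.

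The only layout printed for the 4-well patches is the numbered list in section 5.2.2. It opens with "1: Metals: Nickel sulfate hexahydrate" for Combination #1 and "1: Common metal allergy: Nickel sulfate hexahydrate" for Combination #2.

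On masking, section 5.6 states: "The medical professional that reads the photographs of the test sites will be blinded to all clinical information". It has no matching statement for the in-person assessor. Section 6.3 says of the Day 5 visit that "the medical professional with training in patch testing will review the skin for any reaction and document in the CRF". Section 8.4 gives that assessor the allergen identity of each test site in the event of a reaction.

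Section 7.2.2 then plans to "quantify the agreement of reactions to the same allergens alone (primary test patch) and in combination (secondary test patch"), using kappa. It does not say whose reading supplies the grades.

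**The concern.** There are two separate gaps, and both bear on the same kappa.

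**Layout.** If sites prepare the 4-well patch in the printed order, every wearer of a given version has the same contents in the same well. Any effect of position on that arm could not then be separated from an effect of the mixture. Anyone who knows the version would also know the contents without a key.

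**Masking.** If the kappa uses in-person grades, the assessor grades both arms at one visit with no stated masking, and may have the key for every site once a reaction is seen. An equivocal mixed well could then be graded to agree with its components on the other arm. That pushes agreement up and makes mixing look less costly than it is. The analysis supports the objective in section 2.2 of exploring combinations that lessen the burden of testing, so a bias in that direction favours the conclusion being sought.

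**Working it through.** The plan states no figure on this point, so the check sets the sections side by side.

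**1. Position rule.** Primary patch: four randomised sequences (5.3), and locations randomised between participants (Visit 1 text in section 6). Secondary patch: version by study-number parity (5.3), and placed in a similar manner to the primary (Visit 1). No section states a randomised well order for the 4-well patch, and none states a fixed one.

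**2. What a fixed order would reveal.** Listed order in 5.2.2:

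| Well | Combination #1 | Combination #2 |
|---|---|---|
| 1 | Nickel | Nickel |
| 2 | Balsam of Peru + fragrance mix + quaternium-15 | Balsam of Peru |
| 3 | Neomycin + bacitracin + propolis | MCI/MI |
| 4 | Carba mix + thiuram mix + benzoic acid | Fragrance mix |

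Only well 1 is identical in both. For wells 2 to 4 a reader also needs the version, which follows from the parity of the study number. CRFs identify participants by subject number (9.4).

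**3. Which wells carry the contrast.** Nickel stands alone in both versions, and every well of Combination #2 holds one listed agent or standard mix. New mixtures occur only in wells 2 to 4 of Combination #1.

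**4. How many participants.** Assume consecutive numbering with the sequences repeating: sequence = ((i − 1) mod 4) + 1, and odd i receives Combination #1. For 100 Phase 1 participants this puts 25 in each of sequences 1 and 3 (all Combination #1) and 25 in each of 2 and 4 (all Combination #2). So 25 + 25 = 50 wear Combination #1. Primary sequence is nested in patch version, which is why any secondary well order should be generated separately.

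**5. What matching across arms requires.** The assessor must know what the mixed well holds and which primary sites hold its components. A fixed secondary layout gives only the first. Access under 8.4 covers every site and gives both. The masking gap therefore exists whether or not well order is randomised.

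**6. Direction, by illustration only.** Assumptions not in the documents: sensitivity 0.85 and specificity 0.97 on each arm, one arm-1 reading per well, mixtures losing 25% of reactions, and the 5.2.1 percentages treated as independent positivity rates.

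- Well positivity: 1 − 0.908 × 0.933 × 0.956 = 19.0%; 1 − 0.922 × 0.936 × 0.965 = 16.7%; 1 − 0.942 × 0.972 × 0.963 = 11.8%. Mean 15.85%.
- Proportions: reactive on both arms 0.1585 × 0.75 = 0.1189; lost in the mixture 0.0396; negative 0.8415.
- Cells (arm 1, arm 2): ++ 0.0877, +− 0.0723, −+ 0.0398, −− 0.8002. Observed agreement 0.8879, chance agreement 0.7533, kappa = (0.8879 − 0.7533)/(1 − 0.7533) = 0.55.
- Resolve 30% of discordant gradings toward arm 1: observed 0.9215, chance 0.7467, kappa = 0.69.

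Resolving 20% or 50% gives 0.64 or 0.78. With a 50% loss, kappa is 0.40 with independent readings and 0.54, 0.60 or 0.73 at 20%, 30% or 50%. If each of the three component sites is read separately at 0.85/0.97, the starting values fall to 0.45 (25% loss) and 0.32 (50% loss). The direction follows from the mechanism; the size depends on the assumed inputs.

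**The case against.** A reader might infer that the 4-well patch has a fixed order. The documents do not say so. Section 5.2.1 also numbers the primary allergens, with nickel first, yet their positions are randomised. Sections 3.4 and 5.4 mention randomised allergen locations without limiting them to the primary patch, and the Study Operation Manual that holds the templates is not among the documents. This stands: the text is silent, and a fixed order is only one reading of it. What remains is that the primary patch has an explicit rule overriding its list and the 4-well patch has none.

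A reader might also infer that readers know what every secondary well holds. For the photograph reader that contradicts 5.6, which leaves only the photograph to go on. For the in-person assessor it needs a fixed order plus the version, or access under 8.4.

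Nor do the documents establish that the comparison is unmasked, or that one person's two grades feed it, because 7.2.2 names no reading. They report no position effect on a 4-well forearm patch, and 5.6 links random locations to blinding, not to position effects.

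Finally, this is one secondary analysis under an objective framed as exploration, with no threshold or decision attached. That stands and limits the severity.

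**Conclusion.** The point holds as a minor one. Position randomisation is specified for the primary patch only. If the printed order is used, contents and position are confounded on the secondary patch. Independently, no masking is stated for the in-person assessor, and 8.4 can supply the identities for both arms. If in-person grades feed the kappa, agreement can be inflated.

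The reach is wells 2 to 4 of Combination #1, about 50 Phase 1 participants, and the primary endpoint is not affected. The conclusion is conditional on the printed order being used (layout) and on in-person grades being used (masking). Whether any bias occurs, and how large it would be, cannot be determined from the documents; the kappas above show direction under assumed inputs.

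**What to change.** 1. In 5.6 and 8.4, have the in-person reader record grades for all sites on both arms before the allergen key is opened for grading purposes. This should not restrict any access needed for participant care. It comes first because randomising the wells would not remove the masking gap.
2. In 7.2.2, name the reading that feeds the alone-versus-combination kappa. Repeat the kappa on the blinded photograph reads, with the two arms shown as separate, unlinked images.
3. In 5.3, add randomised well-order sequences for the 4-well patches, generated separately from the primary sequences, and record the order on the CRF.

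The cost is slightly more complex patch preparation, a few more templates, one more CRF entry per participant and protocol wording. No extra participants, readers or visits are needed.

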5.4. Preparation and Application of Test Patches

The application of the allergens to the test patch will be conducted according to the Study Operation Manual. This manual will include the documentation of safe storage and handling practices of the allergens, templates of the randomized allergen locations, and guidelines for the application of the patch to the participant’s arm.

5.5. Subject Compliance Monitoring

The primary compliance consideration for this study is the maintenance of the test patch over the first three days. The participant will be given information on showering and other personal hygiene considerations while the patches are worn. Early removal or contamination of the test patch will be documented on Day 3 during the participant’s visit. Deviations from the expected protocols will be documented on study case report forms.

5.6. Masking/Blinding of Study

The medical professional that reads the photographs of the test sites will be blinded to all clinical information including, but not limited to, the allergen's randomized locations, the in-person assessment of the reactions, and any AI predictions on the images. Effectively, the human read of the photograph will only have the photograph available to form all impressions about the reactions.

The reading of the human interpretation of the photographs will occur at least 1 month after the clinical visit to maintain blinding and washout in the event study staff provide a visual impression of the reaction sites via photographic review.

6. Study Procedures

6.1. Prior to Visit 1 and after study consent, the participant will have an opportunity to complete the Patient Journey. For Phases II and III of the study, this patient journey will be distributed to the patient prior to Visit 1 to allow for the data to be summarized. The summarization will include qualitative and quantitative approaches to quantify the self-reported employment profiles, ancestry, and known allergens to identify which allergens that may be more allergenic to the participant.

Visit 1 (Day 1)

Informed consent will be obtained as well as demographic information, medical history, and current medications questionnaire (see Schedule of Events).

A limited physical exam focused on the forearm will be conducted as well as assessment of participant's Fitzpatrick skin type.

A baseline photo will be taken using the smart phone application and the additional camera systems including the full spectrum documentation and photogrammetry acquisition.

A member of the study team will place the primary test patch on the volar aspect of participants' forearm. The patch contains allergens placed in dime-sized wells. The location of the allergens within the patch will be randomized between participants. The study team member will document the location of each allergen.

The smaller, 4 well patch, on the secondary arm will be placed similar manner to the primary test patch.

Tape or waterproof dressing may be used to secure the patch strips. Participant will be given instructions to avoid water contact with patch, and avoidance of sun exposure.

Participants will be allowed to take over the counter histamine blockers to alleviate pruritus.

6.2. Visit 2 (Day 3)

Participant will be asked to return after 48 hours (Day 3) for patch removal and preliminary reaction assessment.

Skin will be assessed and documented for reactions which may include irritation, redness, and/or swelling localized to the patch test area.

The reaction will be documented as negative, irritation, or positive contact allergic reaction using the scale described below in section 6.6.

Participant will be encouraged to let the study team know if there was any itching or burning while the patches were in place.

A complete set of photos will be taken to document any reactions with the smart phone application and other camera systems.

